3.7.5. Outcomes of the stepped-wedge trial phase

The primary and secondary outcomes for stepped-wedge trial phase are as below.

The study population for the evaluation of the outcomes are the same as the study population in the model optimization phase. See Section 3.6.1 above.

Primary outcome: Proportion of preterm or LBW infants who died during the first 28 days of life (among the trial participants). The primary outcome will be analysed globally in the 24 clusters.

Secondary outcomes (measured in both intervention and control periods)

- Breastfeeding:
 - Proportion of preterm or LBW infants who are exclusively breastfed at discharge from trial facilities
 - o Median age at putting the baby to the breast for the first-time during M-SNCU/SNCU stay
 - Median age at initiation of breastmilk feeding during the M-SNCU/SNCU stay
- Proportion of preterm or LBW infants with clinical sepsis: As diagnosed by the attending physician either defined by clinical signs alone or presence of clinical signs with positive laboratory screening test while in M-SNCU/SNCU
- Proportion of preterm or LBW infants who has hypoglycaemia: Any blood glucose level of <45 mg
 per decilitre, measured when clinically indicated during M-SNCU/SNCU stay, as per the SNCU
 protocol of each study
- Proportion of preterm or LBW infants who has hypothermia: Any axillary temperature <36°C during M-SNCU/SNCU stay
- Proportion of preterm or LBW infants receiving KMC at discharge (8-24 hours of skin-to-skin contact and exclusively breastfed in the 24 hours before discharge) from the trial facility

The coverage, quality and implementation outcomes will be the same as in the model optimization phase, described in section 3.6.2 above. In the stepped-wedged trial the outcomes during the intervention exposure will be compared against the outcomes during control exposure.

The outcome measurement team will collect primary and secondary outcomes through routine health records and registers and/or through interviews with the mother/family.

Implementation outcomes:

During trial phase of the study, we will continue to collect the implementation outcomes monitored during the model optimization phase, and will also collect information related to costs:

- Acceptability: iKMC including transport in skin-to-skin contact from birthing place to M-SNCU is
 acceptable to mothers (and/or surrogates). Mothers and caregivers are satisfied with the care
 received. iKMC is acceptable to health workers (facility and community).
- **Adoption**: The challenges in adoption of iKMC by mothers, hospital managers and health providers (nurses, midwives, doctors) identified in programme learning are addressed.
- Adaptation: Modifications to adapt the iKMC intervention to the social and routine health system context are implemented.
- Cost: what are the costs of implementing iKMC in routine health care settings?
- *Fidelity*: Quality iKMC care is being provided to mothers and newborns in the level 2 M-SNCUs and KMC wards and to what extent the mothers are adhering to the recommended practices.

3.7.6 Measurement strategy

The independent outcome evaluation team will collect data on impact, coverage, and process outcomes:

- Identification of preterm or LBW infants requiring SNCU care. The evaluation team will collect data
 on all preterm or LBW infants admitted to the SNCUs in the study area (all inborn and outborns brought
 in the first 24 hours after birth). They will also record the date and time of birth as well as the date and
 time of admission to the SNCU.
- Ascertainment of vital status: The evaluation team will collect the data on the vital status of all preterm or LBW infants admitted to the SNCUs in trial facilities (i.e., all inborn and outborns brought in the first 24 hours after birth) till discharge and day 28 after birth. This will be done by daily visits to all SNCUs in the trial facilities in pre-discharge period and through telephonic contact on day 28 after birth. The evaluation team will make a home visit if the infant/family cannot be reached on the telephone. The cause of death will be recorded using a standard WHO death certificate for all in-hospital newborn deaths.
- Ascertainment of secondary outcomes. We will strengthen the existing clinical record keeping in the SNCUs and the use of a separate SNCU register wherein the routine SNCU staff will record the key secondary outcomes like breastfeeding, clinical sepsis, hypothermia, and hypoglycaemia. During the daily visits, the study evaluation team will cross-verify the entries in the SNCU register using the clinical records and healthcare provider and/or maternal interviews. The optimal strategy will be worked out during the preparatory phase. Documentation of iKMC will be the same as in the model optimization phase.

The coverage and process outcomes will be measured as described in section 3.6.2. The measurement strategy for the secondary outcomes will be refined based on the learnings from the model optimization phase of the study.

3.7.7. Statistical analysis of the stepped-wedge trial

Sample size and power calculations

The coverage outcomes from the trial will be assessed at the state and country level (to be pooled with data from a similar study in Haryana). The impact outcomes – pre-discharge mortality and NMR, will be pooled at a country level along with Haryana, and ascertained at a global level in combination with data from other countries by the WHO for adequate statistical power.

Due to the paucity of reliable preterm birth data, sample size calculations are based on LBW estimates. The sample size for clusters has been estimated at WHO based on the average characteristics across sites, and is not UP or India-specific. We estimated that an average of 500 LBW newborns (<2 kg) born in a cluster in an iKMC implementing facility(ies) or transferred to the hospital(s) before 24hr from birth per year will be required to ensure adequate sample size. This was calculated based on birth rate of 2%, resulting in estimated 20,000 livebirths. Of which, we assumed that yearly 5% of LBW newborns would require care at SNCU (1000 LBW infants a year). We then assumed that 60% of LBW newborns requiring care at SNCU would be inborn babies or transferred to SNCU within 24 hours after birth (approximately 600 LBW newborns). To allow for varying cluster sizes within country/districts, we have assumed a 0.75 variation coefficient.

Parameter	Estimates
No. of LBW newborns requiring care in level-2 units	500/year (125/quarter)
born in facilities or transferred to facility within 24 hours	
after birth in one district	
Neonatal mortality before discharge in control periods	15%
(based on the WHO immediate KMC trial) [‡]	
Relative mortality reduction	20%
Intra-cluster correlation	0.01 (0.005 to 0.02)
Cluster auto-correlation coefficient	90%
Coefficient of variation of cluster size	0.75

Statistical power calculations consider both the clustered and stepped-wedge nature of the design. To allow for clustering, it is necessary to have estimates of intra-cluster correlations (ICC). We have been guided by patterns and determinants of ICCs as per WHO Global Survey estimations.²² For mortality outcome we have assumed an ICCs of 0.01 (considered sensitivity at 0.005 to 0.02). Considering the

[‡] WHO Immediate KMC Study Group, Arya S, Naburi H, Kawaza K, et al. Immediate "Kangaroo Mother Care" and Survival of Infants with Low Birth Weight. N Engl J Med. 2021 May 27;384(21):2028-2038.

stepped-wedge design, we have allowed for temporal trends as fixed period effects, and additionally to allow for variation in temporal trends across countries (or clusters within countries) we have allowed for cluster-by-period random effects in addition to the cluster random effects. We have therefore incorporated a two-period decay correlation structure with a cluster autocorrelation of 90% in addition to ICCs.

The combined multi-country analysis conducted by the WHO will have 92% power at a 5% significance level to detect a 20% relative risk reduction in neonatal mortality from a baseline of 15% mortality to 12% mortality in the intervention periods. All calculations were done based on a method proposed by Karla Hemming (University of Birmingham, UK) with the Shiny CRT calculator.³¹

With 3 clusters in UP, the total sample size for UP would be around 3,000 LBW births during the 24 months study period. Similarly, with 24 clusters across countries, the total sample size of study would be 24,000 LBW births during the 24 months study period.

Stepped-wedge trial analysis: All analyses will be by intention to treat, which means that clusters will be analysed according to their randomized allocation, i.e., time at which exposure status changed from control exposure to intervention exposure irrespective of whether this was achieved at the desired time. Newborn baseline characteristics will be summarized as means and standard deviations, medians and inter-quartile ranges, or numbers and percentages, as appropriate, grouped by exposure status. The CONSORT guidelines will be followed and a CONSORT trial diagram showing the outcome rate by cluster and by exposure status will be presented.³²

Outcome (rates, proportions, mean/median, as appropriate) will be compared by exposure status (intervention and control). For the primary and secondary outcomes, a multilevel logistic regression model will be used to estimate the effect of the intervention. The binomial distribution and log link function will be considered. The relative risk and the 95% confidence interval will be reported as the effect size estimate. The statistical analysis will adjust for clustering in the data, calendar time, and varying treatment effect between clusters, countries, and with time. We will also consider including the length of the intervention period in the model as an effect modifier. All analyses will be carried out using STATA 14.1. The main analysis will be carried out once all outcome data have been entered into the study database and validated as being ready for analysis. A comprehensive statistical analysis plan will be developed in discussion with the trial statistician. The statistical analysis plan will be written, approved, and finalized prior to the commencement of trial recruitment.

3.8 Promote and support the government to scale up iKMC at provincial and national level

The overarching aim of this project is not only to develop optimized models for iKMC, but to make these models available for scale up nationally and internationally to reduce newborn morbidity and mortality. The project will have established both the necessary evidence base for scaling up iKMC, as well as the necessary resources, tools, materials, and strategies to do so. Assuming effectiveness, this will become the established international standard by which iKMC can be adopted and optimized across all settings. We would also have addressed questions of scalability related to scale up approach, capacity, and investment. Above all, the government would already have had the experience of implementing iKMC in multiple districts as well as observed its benefits.

Accordingly, a scale-up strategy will be develop in close consultation with the state and national government with the research team providing the necessary technical support. This is in alignment with the ongoing scale-up of KMC in UP. Findings from the study will be consolidated by the WHO with findings from other countries to propose a global model for scaling up immediate KMC. WHO will also involve the STAGE-MNCAH&N-KMC Working Group, which is a multi-partner group in these efforts.

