The impact analysis will be conducted as a pooled analysis of data from all the countries. A sample size of 500 low birth weight newborns per year per district, i.e. 1000 newborns per district over the 24 months study period, would yield a total of 24,000 newborns across all the study sites (4 countries with 6 districts each). The combined multi-country analysis conducted by the WHO on this sample will have 92% power at a 5% significance level to detect a 20% relative risk reduction in neonatal mortality from a baseline of 15% mortality (i.e. 150 per 1000 livebirths in this population) to 12% mortality (i.e. 120 per 1000 livebirths) in the intervention periods. The data management across all the global sites will be done by the Translational Health Science and Technology Institute (THSTI), an autonomous institute of the Department of Biotechnology, Ministry of Science & Technology, Govt. of India. THSTI will develop a common data platform for both phases of the study, which will be adapted as per the needs of each site. The data for the UP site will be stored on a cloud server managed by CEL, and clean, de-identified data will be shared with the WHO for review and feedback at regular intervals.

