3.7.2 Evaluating the impact of the scale-up: stepped-wedge cluster RCT design

The impact of the scale-up of the optimized model on neonatal mortality will be evaluated in a stepped-wedge, cluster-randomised trial design in 3 districts over a 24-month duration (Figure 8). The unit of randomization will be a district with 1-2 facilities having functional level 2-SNCUs that provide a minimum package of small and sick newborn care. Each cluster will be randomized sequentially to implement the optimized iKMC model.

Figure 10. Roll-out of the stepped wedge cluster RCT design in UP

#	Υ0	Y1-Q1	Y1-Q2	Y1-Q3	Y1-Q4	Y2-Q1	Y2-Q2	Y2-Q3	Y2-Q4
Cluster 1	Minimum	С	т	1	1	1	I	ı	1
Cluster 2	Care Package for small babies	С	С	С	Т	ı	ı	ı	ı
Cluster 3	implemented	С	С	С	С	С	т	ı	1

C= Refers to control period in which small or sick newborn care is strengthened.

T= Refers to transition period (no measurement)

I= Refers to intervention period in which the iKMC implementation model scaled up

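### The stated 92% power and 24,000 infants match eight measured quarters per cluster, but Figure 10 leaves one unmeasured; as drawn, the design gives 21,000 infants and about 80% power

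*Protocol*

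**What the plan says.** **Power.** Protocol section 3.7.7 states: "The combined multi-country analysis conducted by the WHO will have 92% power at a 5% significance level to detect a 20% relative risk reduction". The outcome is neonatal death, and the effect assumed is a fall from 15% under control to 12% under the intervention. The opening summary repeats the claim.

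**Sample size.** Section 3.7.7 says "the total sample size of study would be 24,000 LBW births during the 24 months study period", with around 3,000 of these in UP. The summary gives the same rate per district: "i.e. 1000 newborns per district over the 24 months study period".

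**Inputs.** The parameter table in section 3.7.7 gives a cluster size of "500/year (125/quarter"), an ICC of "0.01 (0.005 to 0.02"), a cluster autocorrelation of 90% and a coefficient of variation of cluster size of 0.75. The text adds fixed period effects and random effects for cluster and cluster-by-period. It also calls this a two-period decay structure.

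**Design.** Figure 10 (section 3.7.2) shows eight quarters for each of three UP clusters. One quarter per cluster is coded T, and the legend reads "T= Refers to transition period (no measurement"). The text below the figure confirms a three-month transition in each cluster.

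**The concern.** The stated totals equal eight quarters of recruitment per cluster, while the figure that defines the design leaves only seven with data. The sample-size text does not mention the transition.

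The effect on power is more than proportional. In a stepped-wedge design much of the information about the intervention lies in the cells next to each cluster's crossover, and those are the cells removed. Section 3.7.7 justifies pooling across countries by the need for adequate power. If the true figure is about 80%, a null result would be read with more confidence than the design supports.

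**Working it through.** **1. Sample size.**

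| Quarters counted | Per cluster | UP (3 clusters) | All 24 clusters |
|---|---|---|---|
| Eight | 8 x 125 = 1,000 | 3,000 | 24,000 |
| Seven (T unmeasured) | 7 x 125 = 875 | 2,625 | 21,000 |

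The protocol's figures are those in the first row.

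**2. Power: inputs.** From section 3.7.7: 15% vs 12% (difference 0.03), 125 per cluster-quarter, ICC 0.01, cluster autocorrelation 0.9, coefficient of variation 0.75, fixed quarter effects, 24 clusters. From Figure 10: the three sequences C T I I I I I I, C C C T I I I I and C C C C C T I I. Two assumptions are added: eight clusters per sequence (only the UP roll-out is drawn) and a two-sided 5% test (sidedness is not stated).

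**3. Power: formulas.**
- Individual variance: s² = (0.15 x 0.85 + 0.12 x 0.88) / 2 = 0.11655.
- Correlation between two infants in one cluster: 0.01 in the same quarter, 0.01 x 0.9 = 0.009 in different quarters.
- Covariance of the cluster-quarter means for a cluster with m infants per quarter: s² x [R + I x (1 − 0.01)/m]. R has 0.01 on the diagonal and 0.009 elsewhere, and I is the identity matrix.
- The variance of the effect is the treatment element of the inverse of the summed X'V⁻¹X, where X holds the quarter indicators and the treatment indicator. Unmeasured cells are left out.
- Power = Φ(0.03/SE − 1.96). Unequal cluster sizes are drawn from a gamma distribution with coefficient of variation 0.75 and averaged over several hundred draws.

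**4. Reproducing the stated figure (all eight quarters).** SE is about 0.0089. Then 0.03/0.0089 − 1.96 = 1.41, so power is about 92%. The result is the same whether the transition quarter is coded as control or as intervention. A simulation with binary outcomes gave 92.0%. The protocol's 92% reproduces.

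**5. Figure 10 as drawn (T removed in its calendar place).** SE is about 0.0107. Then 0.03/0.0107 − 1.96 = 0.84, so power is about 80%. The simulation gave 79.9%.

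**6. Sensitivity.**

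| Setting | Eight quarters | T unmeasured |
|---|---|---|
| Central inputs | 92% | 80% |
| Equal cluster sizes | 94% | 83% |
| ICC 0.005 | 94% | 84–85% |
| ICC 0.02 | 87–88% | 73–75% |
| Discrete-time decay, 0.9 per quarter | 85–86% | 70% |
| Six crossover steps instead of three | 94% | 81–82% |

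Ranges reflect repeated calculations with different random cluster sizes.

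**The case against.** Several points can be made for the protocol.

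**The calculation was not built on the UP figure.** Section 3.7.7 says the sample size was worked out at WHO on average site characteristics, and Figure 10 is titled for UP. This stands as a limit on precision: the 80% assumes that all 24 clusters follow the UP roll-out. It does not remove the gap, since a six-step layout gives about 82% with the transition unmeasured.

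**24,000 may be an accrual count.** The text speaks of births during the study period, and the derivation reaches about 600 per year per cluster before settling on 500. Seven quarters at 150 give 1,050 per cluster, so 24,000 measured infants are attainable. Power is then about 85%, still short of 92%.

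**The year before the trial might supply control data.** Adding four such quarters as control time brings power to about 85%. The stated 24,000 leaves that year out.

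**The transition may be measured after all.** Sections 3.7.6 and 4.2.3 collect vital status on all eligible SNCU admissions and make no exception for the transition. The intention-to-treat statement in section 3.7.7 does not mention it either. This is a real conflict with Figure 10, so the remedy must allow for either resolution.

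**80% is a conventional power level.** True, and nothing here shows the trial to be unsound. The fault is that the stated figure does not belong to the stated design.

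A reader might also infer that 92% could have been obtained only by counting the transition quarter. The documents do not show how the sponsor computed it. Closing up the seven measured quarters as if they were aligned across clusters gives about 90% (92.5% with equal cluster sizes) without counting T, although that is not Figure 10's calendar layout.

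A reader might further infer that the 15% baseline is wrong, because the parameter table labels it "Neonatal mortality before discharge in control periods" while the primary outcome is death within 28 days. That is unsupported. A pre-discharge rate would understate 28-day deaths, heavier sick infants could move the rate the other way, and section 3.1 selects UP districts on neonatal mortality of at least 15% in infants under 1800 g. The direction is undetermined, so this is only a labelling question.

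**Conclusion.** The stated power and sample size do not match the design as drawn. No setting tried that keeps Figure 10's calendar, leaves the transition unmeasured and uses the protocol's inputs comes back to 92%.

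The sample-size part needs only multiplication: the totals exceed the measured number by 3,000 infants overall and 375 in UP. The power part, a loss of about 12 percentage points, rests on three assumptions: every cluster follows the UP sequences, the test is two-sided, and the correlation structure is cluster plus cluster-by-period effects. Confidence is high that the figures are inconsistent and lower for the exact replacement. About 80% is the central value, with 73–85% over the protocol's ICC range and about 70% under discrete-time decay.

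**What to change.** In the summary and section 3.7.7, restate the measured sample size as about 21,000 (2,625 in UP) and the power for 15% vs 12% as about 80%. Name the correlation structure, state the roll-out assumed for the 24 clusters, and give the sensitivity range, including the decay case if that structure is intended.

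If the transition quarter is to be measured, correct Figure 10 instead, state how that quarter enters the analysis, and give sample size and power to match.

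As a minor addition, say in the parameter table whether the 15% is pre-discharge or 28-day mortality.

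The change is to wording in two paragraphs, plus the parameter table or the figure legend. The price is a less favourable stated power.

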3.3 Study population

Newborns: The study population is preterm or LBW newborns (gestational age <37 weeks or birthweight<2.5 kg) (requiring care in the SNCU, i.e., weighing <1800 grams at birth, or those preterm or LBW newborns who weigh >=1800 grams but are sick and need SNCU admission. See Figure 6 below.

The revised WHO guidelines include a recommendation for KMC for all preterm or LBW infants starting immediately after birth unless the newborn is critically sick.²⁶ Therefore, KMC provision for all preterm or LBW infants will be strengthened at all levels of care.

However, the purpose of the study is to implement and scale up iKMC for preterm or LBW infants **who are at high risk of being separated from the mother**, i.e., those preterm or LBW infants who require NICU/SNCU care, either because they are too small or sick. Hence, while the study will promote and strengthen immediate KMC for all preterm or LBW infants, the study population will only comprise of preterm or LBW infants who require NICU/SNCU admission after birth as depicted in Figure 6. During the intervention period, these infants will be admitted to M-NICU/SNCUs where their mother/surrogate will stay with them on a 24x7 basis and will be supported to provide KMC. During the control periods, these infants will be admitted to the normal/routine NICU/SNCU and KMC will be promoted and encouraged through existing mechanisms.

Figure 6 - Description of study population

The population eligible for outcome evaluation is described in Section 3.6.1

Health workers: Health workers (and managers) working at the participating sites will be the target of community-, facility- and provider-level components of the iKMC implementation models.

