The stepped-wedge design is a unidirectional crossover design where all clusters start in the control phase (i.e., minimum package of care for small and sick newborns) and cross over to the intervention (i.e., the optimized iKMC implementation model) at different timepoints, till all clusters have transitioned to the intervention condition. All 3 clusters in the state will start with the control condition (see Figure 10). At each equally spaced cross-over time, one cluster will transition to the immediate KMC implementation model based on a pre-allocated random sequence. A three-month transition period is included in each cluster to allow for the implementation model to be operationalized. All the implementation strategies which are part of the optimized model will be implemented during this period. Briefly, these will include infrastructural changes (e.g., M-SNCUs), supplies (e.g. KMC beds, chairs, and garments), staff training and supervision, monitoring and feedback in the immediate KMC implementing facilities, and strengthening of newborn care to ensure early identification and referral of eligible infants to the immediate KMC implementing facility in skin-to-skin contact with the mother or surrogate, and strengthening of referral pathways. Once each cluster has crossed to the intervention, it will continue to be exposed to it for the remaining duration of the study. The coverage outcomes will be analyzed at the state and country level (along with another similarly designed study to be conducted in Haryana). However, impact outcomes, i.e., pre-discharge and neonatal mortality will be pooled and analyzed at the country level (along with another similarly designed study to be conducted in Haryana) and ascertained at a global level in combination with data from multiple countries by the WHO.

The rationale for a stepped-wedge design in evaluating the effectiveness of the optimized implementation model is as follows:

- There are clear benefits to the use of iKMC for newborns. Therefore, it is important for the governments/ ministries /policymakers and the local healthcare providers involved in this implementation research study to be assured that no districts/patients are denied improved access to iKMC because of being part of a research project. Through this design, they can participate in a randomized trial and all clusters can be guaranteed to receive the intervention.

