We will strengthen the existing clinical record keeping in the SNCUs and the use of a separate SNCU register wherein the routine SNCU staff will record the key secondary outcomes like breastfeeding clinical sepsis, hypothermia, and hypoglycaemia. During the daily visits, the study evaluation team will cross-verify the entries in the SNCU register using the clinical records and healthcare provider and/or maternal interviews. The optimal strategy will be worked out during the preparatory phase. For documentation of continued KMC post-discharge, the outcome evaluation team will administer a pre-tested questionnaire to the mother telephonically on day 29. Documentation of iKMC implementation will be similar as in the model optimization phase.

Detailed information on definitions, numerator, and denominator for each outcome in the model optimization phase is described in the Table 4, however it is important to note that the measurement strategy for the secondary outcomes will be refined based on the learnings from the model optimisation phase.

Table 4. Definitions, numerators, and denominators of outcomes in stepped-wedge trial phase

Table 4. Delimitions, numerators,	and denominators of out	отпев ит втерреи и	eage that phase	
	Numerator and denominator	Specific notes to the	Data collected by	
		indicator	Who	How and where
Primary outcome to be measi	ured in both intervention	and control perio	ods for each stu	dv cluster
Proportion of preterm or LBW infants who died during the first 28 days of life (among trial participants)	Numerator: Number of neonatal deaths by 28 days of age Denominator: Number of preterm or LBW infants admitted in the M-SNCU/SNCU in the trial facilities (Expressed as percentage or rate per 1000 livebirths)		Outcome evaluation team	By daily visits to M- SNCU/SNCU until discharge, and through telephone contact on day 29 of age post- discharge
Secondary outcomes to be m measurement strategy will be	easured in both interver			study cluster (the
Breastfeeding outcomes:			First outcome will be	Using hospital registers and
Proportion of preterm or LBW infants who are exclusively breastfed at discharge from trial facilities	Numerator: Number of preterm or LBW infants who are exclusively breastfed Denominator: Number of preterm or LBW infants admitted		measured by the outcome evaluation team	maternal interviews

	Numerator and denominator	Specific notes	Data	collected by
	denominator	indicator	Who	How and where

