5.2 Risk

There might be a risk of poor outcome of a baby if s/he is preterm or LBW babies and unstable, however there will be well-equipped establishment of M-SNCU run by thoroughly trained staff, with continuous monitoring system, hence risk will be mitigated.

There might be a risk that mothers/caregivers feel that the poor outcome of their children is due to failure to seek care, non-compliance with treatment, or lack of money. However, the healthcare providers will be well trained in asking these questions to mitigate the risk.

The unavailability of mothers/caregivers willing to provide consent might be a recruitment barrier due to maternal illness or post-caesarean section and the absence of other family members at the hospital during the early admission period. The health workers will be well trained in counselling of the family member for providing the iKMC in the absence of mother. Hence this risk will be mitigated. Community engagement will also help mitigate this risk by creating awareness regarding iKMC and the potential need for surrogates.

There might be a risk of being overloaded of preterm or LBW newborns in the iKMC implementing facility because of efforts to strengthen the referral system. We will strengthen the capacity of the iKMC implement facility to provide the WHO minimum care package for preterm or LBW newborns.

6. Study governance

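### The stated adjustment set names no infant-level covariate, although the package can change which infants are admitted at each cluster's crossover, so a case-mix shift can mimic or hide a mortality effect

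*Protocol*

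**What the plan says.** Section 3.7.7 gives the model and its adjustment set: "For the primary and secondary outcomes, a multilevel logistic regression model will be used to estimate the effect of the intervention", and then "The statistical analysis will adjust for clustering in the data, calendar time, and varying treatment effect between clusters, countries, and with time". Baseline characteristics are to be summarised by exposure status, descriptively. The section also states that "A comprehensive statistical analysis plan will be developed in discussion with the trial statistician" and that this plan will be final before recruitment starts.

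The primary outcome is death in the first 28 days. Its denominator in Table 4 (section 4.2.3) is "Number of preterm or LBW infants admitted in the M-SNCU/SNCU in the trial facilities". Section 3.3 puts two groups in the study population for Uttar Pradesh: infants below 1800 g, and "those preterm or LBW newborns who weigh >=1800 grams but are sick and need SNCU admission". Section 3.6.1 has the same structure with a country-specific cut-off.

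Section 3.7.2 lists what is put in place in each cluster's three-month transition. Besides unit conversion, supplies and training, it names "strengthening of newborn care to ensure early identification and referral of eligible infants to the immediate KMC implementing facility" and better referral pathways. Section 5.2 lists a "risk of being overloaded of preterm or LBW newborns in the iKMC implementing facility because of efforts to strengthen the referral system". Arrival within 24 hours of birth is a quality outcome (section 3.6.2), and section 3.7.5 carries it into the trial phase for comparison between exposures.

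**The concern.** Exposure and intake can change together. The package is meant to bring more eligible infants to the unit sooner, and infants are counted after they arrive. Above the cut-off, staff who know the cluster's exposure decide who is sick enough for admission. Mortality among admitted infants can then move because the infants differ, with no change in any infant's chance of survival.

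At stake is the reading of the primary result. Extra low-risk admissions would look like benefit. Extra high-risk infants who now arrive alive would look like harm or mask a real benefit.

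**Working it through.** **Target effect.** Section 3.7.7 plans for 15% falling to 12%: 1 − 12/15 = 20%, a relative risk (RR) of 0.80. The sizes below are set against this.

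**Why the stated terms do not remove a shift at crossover.** In the third quarter of year 1 (Figure 10), cluster 1 is under intervention and clusters 2 and 3 are still control.
- A cluster term removes differences that are constant over time within a cluster.
- A calendar-time term removes changes common to all clusters in that quarter.
- A change that starts in each cluster at its own crossover follows the same pattern as the exposure indicator, so it goes into the exposure coefficient.
- Letting the treatment effect vary by cluster, country or time lets the apparent effect vary. It does not separate case mix from effect.

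**Illustration 1: shift in weight mix, no true effect.** Assumed inputs: mortality 19% below 1800 g and 6% at or above, with 70% of control-period admissions below 1800 g. They are chosen so that control mortality is close to the protocol's 15%. Mortality = h × 0.19 + (1 − h) × 0.06, where h is the share below 1800 g.

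| h | Mortality | Apparent relative reduction |
|---|---|---|
| 0.70 | 0.133 + 0.018 = 0.151 | – |
| 0.65 | 0.1235 + 0.021 = 0.1445 | 4.3% |
| 0.60 | 0.114 + 0.024 = 0.138 | 8.6% |
| 0.55 | 0.1045 + 0.027 = 0.1315 | 12.9% |

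With a flatter assumed gradient (18% and 8%), the 10-point shift moves mortality from 15.0% to 14.0%, a 6.7% reduction. If h rises instead, the sign reverses.

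**Illustration 2: extra admissions, no true effect.** From the protocol: 15% control mortality, and 60% of infants needing unit care being inborn or transferred within 24 hours (both section 3.7.7). Let E be the extra admissions as a share of control-period intake and q their mortality. Apparent RR = [(0.15 + E·q)/(1 + E)]/0.15.
- Capture rising from 60% to 70% (assumed): E = 10/60 = 1/6. RR is 0.90 at q = 5% (assumed) and 1.09 at q = 24%, the neonatal mortality that section 1 reports for infants below 2000 g in an earlier Uttar Pradesh study.
- Capture rising from 60% to 80% (assumed): E = 20/60 = 1/3. RR is 0.83 at q = 5%, 1.15 at q = 24%, and 1.25 at q = 30% (assumed).
- At q = 15%, RR is 1.00: more admissions alone do no harm, only a different risk mix does.

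If a true RR of 0.80 applied to all infants alike, a case-mix factor of 1.15 would show it as 0.80 × 1.15 = 0.92.

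**The case against.** The strongest objection is that covariates belong in the statistical analysis plan, which is not shown, and that section 3.7.7 does not call its list complete. A reader might infer that the analysis adjusts for nothing but clustering and time. The text does not support that: it also names varying treatment effects, and infant covariates may yet be added. What remains is that the protocol states an adjustment set, and as stated it leaves out the factor that the protocol's own package can change.

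Second, no passage shows that case mix shifts at crossover. Section 3.5.4 puts access and referral work before iKMC starts, sections 3.7 and 3.7.1 strengthen unit care before the evaluation, and the overload risk in section 5.2 is not tied to crossover. This may shrink the shift. It does not rule one out, because section 3.7.2 still lists identification and referral among what is put in place at crossover. Leaving the transition quarter unmeasured does not help if the new intake persists afterwards.

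Third, referral is part of the package, so its consequences might be called part of the effect. That would hold for mortality among all births. Among admitted infants, a change in composition is not lives saved or lost.

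Fourth, inborn infants below the cut-off might seem immune. They are not: Figure 9, section 4.1.2 and section 9.1 include referring at-risk pregnant women to the implementing facility or a higher-level hospital, so the inborn group can change too. Clinical judgement also reaches small infants through the exclusions in section 3.6.1. The 1800 g cut-off is Uttar Pradesh's, whereas section 3.6.1 uses country-specific ones.

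**Conclusion.** The point holds in a limited form. The stated adjustment set has no infant-level term, the package includes referral work timed to crossover, and the denominator is admitted infants. A case-mix shift at crossover can therefore be read as a mortality effect or can hide one. That it *will* be so read is a stronger inference, and the documents do not support it: neither the occurrence, the size nor the direction of a shift is known.

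Under the assumed stratum mortalities, shifts of 5 to 15 points give roughly 4% to 13% relative, which is part of the 20% target and not all of it. The larger values in the second illustration need capture to rise from 60% to 80% and the added infants to have a risk well away from 15%. Bias towards no effect is as open as bias towards benefit.

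**What to change.** - **Primary model:** prespecify adjustment for birth weight, and for gestational age where reliably recorded, keeping the cluster and period terms. Birth weight is fixed before skin-to-skin contact begins, so adjusting for it removes none of the effect on a given infant.
- **Sensitivity 1:** the same model without these covariates, also reported as a relative risk.
- **Sensitivity 2:** additional adjustment for inborn/outborn status. Keep this out of the primary model, because maternal referral under the package can change it.
- **Sensitivity 3:** inborn infants below the country's admission cut-off, described as less exposed to the bias but not free of it.
- **Description:** tabulate birth weight, gestation and inborn share by exposure and by quarter. Section 3.7.7 already plans a summary by exposure.

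The cost is small. Eligibility and the admission cut-off rest on birth weight, and section 4.2.2 describes its collection in the model optimisation phase. Gestational age is less secure: an infant can qualify on weight alone, and section 3.7.7 notes that reliable preterm birth data are scarce. The downside is slightly more analysis work. Adjustment removes only the part of a shift that the measured covariates capture; a change in how sick the admitted infants are at a given weight would remain.
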